Study Protocol

The development of an online intervention to reduce HIV/STI risk and drug use-related harms among stimulant-using MSM in Malaysia

Version 2.1 08/03/2022

Planned Study Period: 1 December 2020 – 30 June 2022

Sponsor : Malaysian AIDS Council

Funders : Global Fund to Fight AIDS, Tuberculosis and Malaria

Sustainability of HIV Services for Key Populations in Asia Program

(SKPA)

Investigators : [name]

Department of Social and Preventive Medicine,

Faculty of Medicine, University of Malaya.

Associate [name] [name]

Department of Psychological Medicine,

Faculty of Medicine, University of Malaya.

ISTCTN : 14406171

Study Synopsis

Study title	The development of an online intervention to reduce HIV/STI risk and
	drug use-related harms among stimulant-using men who have sex with men (MSM) in Malaysia
Sponsor	Malaysian AIDS Council
Funder	Global Fund to Fight AIDS, Tuberculosis and Malaria
Tunder	Sustainability of HIV Services for Key Populations in Asia Program (SKPA)
ISRCTN	14406171
Project Start Date	December 2020
Project End Date	June 2022
Research Aspect	The study will develop a community-based, online intervention to cater
1	the mental health and sexual health needs for stimulant-using MSM in Malaysia. Participants are able to access harm-reduction information, support for drug use recovery, as well as peer counselling on sexual risk reduction at their own privacy and convenient time. The study builds the capacity of community-based organization in reaching stimulant-using MSM and provide evidence-based, psychosocial support to these men who are vulnerable to a range of adverse health outcomes, including depression, suicidality, HIV/STI/Hepatitis C & B Infection.
Objectives	To develop an online intervention for stimulant-using MSM in Malaysia
3	and collect feasibility and efficacy data
Study Design	Randomized control trial.
Sample Size	226 men aged at least 18 years who eEngaged in chemsex with other men (defined as using crystal methamphetamine, GBL/GHB, or ecstasy/MDMA) in the past 12 months
Intervention and	Participants will be randomly allocated to two groups:
control groups	, , , , , , , , , , , , , , , , , , ,
	Group A (Intervention Group Group A will receive the developed intervention tool comprising a Brief Intervention (FRAME Model). An online meeting will be arranged with a trained, peer counsellor to discuss drug use behaviour and to provide support and motivation to change. After the brief counseling, participant will then be directed to the Chemsex Care Plan, a self-directed interactive program that participants can access anytime at their convenience and will provide participants access to online materials (videos, infographics, etc) to educate stimulant-using MSM on reducing risky drug-use behaviour, as well as goal-setting. Participant will be asked to complete a brief survey at 6-week and 12-week follow-up to assess the drug use behavior and motivation to change.
	Group B (Control Group) Group B will receive a self-help toolkit from the World Health Organization for cutting down and stopping drug use. Participant is encouraged to use the toolkit to manage their drug use for 12 weeks. Similar to Group A, they will then be asked to complete a follow-up survey after 6 weeks and 12 weeks. After the end of the study, they will be given access to the Chemsex Care Plan.

	Randomization							
	Participants who agree to the follow-up study are sent a link and a							
	password (unique password for each participant) to log onto the study							
	website. Those logging on are randomized in 1:1 ratio with no							
	stratification to receive their respective materials.							
Study outcomes	The development of the online intervention addresses the worsening HIV							
	epidemic in a subpopulation of MSM in Malaysia. This pilot study							
	collects the feasibility, acceptability, and preliminary efficacy of ASSIT-							
	Brief Intervention and Chemsex Care Plan to reduce harms related to							
	drug use and sexual risk among MSM.							
Measurements	Primary outcome measure							
	Stimulant use severity is measured using e-ASSIST (eASSIST; measured							
	at baseline and 12-week follow-up)							
	- /							
	Secondary outcome measures							
	Measured at baseline, 6-week, and 12-week follow-up:							
	1. Number of days stimulants used in the last 30 days							
	2. Depression, Anxiety, and Stress Scale - 21 Items (DASS-21)							

Project Summary

The proposed study aims to develop a community-based, online intervention to address the mental health and sexual health needs among stimulant-using MSM in Malaysia. Recreational drug use in the sexual context ("chemsex") is driving the HIV epidemic among MSM in Malaysia and yet community-based, harm-reduction services are not available for MSM who wish to reduce their drug use or support their recovery from drug abuse. In this pilot study, participants will be able to receive peer counselling on drug use and sexual risk reduction, access interactive online education materials to support their recovery, at their own privacy and convenient time. The psychosocial interventions selected for the study (ASSIST-Brief Intervention and Chemsex Care Plan) are rooted in motivational interviewing which is client-oriented and aims to enhance participants' motivation in changing drug use and risky sexual behaviors, and helps participants establish and meet their goals in reducing both behaviors. This pilot randomized controlled trial will provide feasibility, acceptability, and efficacy of a community-led online intervention to reduce harms associated with stimulant use among MSM in Malaysia. Specifically, this online intervention will address HIV/STI/Hepatitis risk and a range of adverse mental health conditions such as depression, suicidality, and harms related to methamphetamine overdose and methamphetamine-induced psychosis. This brief and portable intervention for stimulant-using MSM will build on the strength of a previous successful sexual health campaign for MSM, and will be integrated with the prevention services at the HIV NGOs and mental health services in Malaysia.

Table of Contents

STUDY SYNOPSIS	2
PROJECT SUMMARY	4
1. INTRODUCTION	6
BACKGROUND	7
2. MATERIALS AND METHODS	9
2.1 STUDY PARTICIPANTS AND DATA COLLECTION	9
2.2. STUDY INSTRUMENTS	10
2.3. RANDOMIZATION, EXPERIMENTAL CONDITIONS AND FOLLOW-UP	11
2.4. SAMPLE SIZE ESTIMATE	11
2.4. Data analysis	12
2.4.1. Outcome variables	12
2.4.2. Analysis plan	12
3. ONLINE INTERVENTION	14
3.1 Brief Intervention (FRAMES model)	15
3.2 THE CHEMSEX CARE PLAN.	17
4. ETHICAL CONSIDERATIONS	18
5. ADAPTATION PROCESS	19
APPENDICES	21
DEFEDENCES	20

1. Introduction

Sexualized drug use has become a growing concern in the MSM communities globally (Bourne et al. 2015, Schmidt et al., 2016) and in southeast Asia (Lim SH, et al., 2015; Vu NT. Holt M et al. 2016). The is a clear association between stimulant drug use among MSM and the risk of HIV infection (Vu NT, 2015). In Malaysia, the use of stimulant drugs by some MSM to facilitate and enhance sexual pleasure has been documented (Lim et al., 2018). In a qualitative study of stimulant-using MSM, sexual disinhibition and hypersexuality was common during chemsex, leading to decreased condom use, sex with multiple partners and other high risk sexual behaviors that increased the likelihood of HIV and STI transmission. MSM who have problematic use suffer from a range of physical, mental, and social harms associated with stimulant use (Lim et al., 2018). Despite draconian drug laws in Malaysia, crystal methamphetamine, ecstasy and GHB/GBL were among the popular drugs for chemsex. The normalization of stimulant drug use can be observed in gay dating apps and social media where stimulant-using MSM seek for chemsex partners and to trade stimulant drugs.

The prohibition of drug use and homosexuality in Malaysia has marginalized this subgroup of MSM. Drug treatment services tailored to the needs of MSM are non-existent in Malaysia. A community-based, low-threshold, online intervention that provides a safe environment where MSM access drug screening, harm-reduction materials is needed. Therefore, we propose to develop a comprehensive online intervention that will address the sexual health and mental health needs of stimulant-using MSM in Malaysia. In this interactive website, clients will be able to access harm-reduction materials, undergo screening for substance use and be provided with a brief intervention virtually by case workers. ASSIST (The Alcohol, Smoking and Substance Involvement Screening Test) plus brief intervention, has been developed by the World Health Organization to identify and treat substance use disorders (WHO, 2010). It has been translated and validated in Bahasa Malaysia. In the proposed study, the outreach workers from the community-based organizations will be trained to administer ASSIST in order to screen MSM for stimulant drug use and deliver a brief intervention using motivational interviewing techniques. The screening and administration of the brief intervention will be conducted synchronously online with the clients. Additionally, risk reduction related to HIV/STI will be included in the brief intervention. MSM who are unaware of their HIV status will be encouraged to undergo HIV testing at the MSM-friendly clinic. Those who test negative will be linked to PrEP services for HIV prevention. Likewise, MSM who test positive will be supported for linkage to care and initiation of antiretroviral therapy. For MSM who have been diagnosed with HIV prior to the study, they will be supported to take their ART to achieve viral suppression.

MSM who do not wish to interact with CBO workers online will have to option to use the electronic version of ASSIST to self-evaluate the frequency and severity of their drug use. Subsequently, they will be linked to **Chemsex Care Plan**, an online tool which enable users to select the best strategies to manage their drug use according to their short-term and long-term life goals (Stuart D & Weymann 2015). The Chemsex Care Plan consists of interactive

online materials designed to help MSM explore their motivation for change, to learn harm-reduction information for those who are not ready to reduce or quit using, and cognitive skills to prevent relapse for those who wish to be abstinent from using drugs. This online tool will be helpful for MSM who wish to access health education materials and learn some cognitive and behavioral skills on their own. The content of the videos available in Chemsex Care Plan reflects the realities of gay men struggling with drug abuse in the UK and these videos have raised awareness on the severity of chemsex in the MSM communities in the UK and provided practical advice in supporting MSM in recovery.

In the proposed study, all ASSIST materials will be adapted to include sexual risk reduction, and HIV/STI/Hepatitis C prevention. Secondly, the content of The Chemsex Care Plan will be translated to Bahasa Malaysia and to develop videos that are culturally appropriate to Malaysian contexts. A webmaster will be hired to design an interactive webpage. The aims of the present study are:

Aim 1: To adapt ASSIST-brief intervention, Chem Sex Care Plan to reduce drug use and HIV sexual risks for stimulant-using MSM in Malaysia

Aim 2: To determine the feasibility and efficacy of an online intervention for stimulant-using MSM in Malaysia.

Background

Stimulant drug use may be driving HIV epidemic among MSM in Asia.

The HIV epidemic among MSM is escalating in Asia and the Pacific region, with increasing HIV prevalence among MSM in Thailand (van Griensven 2013), China (Ma 2007), and Malaysia (MOH 2018). The national HIV prevalence among MSM was 21.6% in Malaysia, among the highest in the region. In a cohort study of 1744 Thai MSM, the increase of HIV prevalence was parallel to the increase with the use of stimulant drugs (Piyara P, van Griensven et al, 2018). Young age, finding casual sex partners on the internet were associated with both incident methamphetamine use and HIV infection (Piyara P, van Griensven et al, 2018). In an anonymous online survey, 7.6% of Malaysian MSM reported using poppers, crystal methamphetamine, erectile dysfunction in the past 6 months (Lim et al. 2015). Men in the stimulant drug use were 3.9 times more likely to be HIV positive and were more likely to have engaged in group sex and have had more than 6 sexual partners in the past 6 months (Lim et al 2015).

Chemsex is an emerging issue with growing concerns among MSM communities in Asia. The use of specific drugs to enhance sexual pleasure and to prolong sexual activities among MSM has been known as 'chemsex'. In the UK, chemsex is defined as the use crystal meth, mephedrone and GHB/GBL before or during sexual activities among MSM. In Asia-Pacific region, the prevalence of chemsex ranges differently according to countries, from 5% in Japan, 9.3% in Taiwan, 11-14% in Australia, to nearly 18% in Thailand. In the previous online surveys of Malaysian MSM, the prevalence of chemsex range from 13.7%% (Lim et al.

2015) to 17.2% (Lim et al. 2017). Besides HIV and STI infection, MSM who engage in chemsex are vulnerable to mental health and social consequences associated with stimulant drug use (Lim et al 2019). Sexual disinhibition and heightened sexual arousal may lead to adventurous sex and extreme sex, limiting ability of MSM in practicing safer sex. In a qualitative study of stimulant-using MSM living in Klang Valley, participants reported that sleep deprivation, poor dental health, weight loss, increased palpitation, hallucination, depressed mood, and psychosis as the short-term and long-term effects of stimulant use.

A community-based, online intervention may be effective in reaching stimulant-using MSM. Due to cultural and legal prohibition of same-sex activities and illicit drug use in Malaysia, stimulant-using MSM are marginalized and hidden (Lim et al, 2018). Many MSM who have stimulant use problems do not seek help or treatment to address their drug use problems. Some may not be aware of the available psychiatric and substance abuse services in Klang Valley and other parts in Malaysia. These services may be limited as the providers may not be familiar issues surrounding sexual orientation and the health needs of MSM. Due to cultural and legal prohibition, perceived stigma and discrimination against gay men in the healthcare settings remain prevalent in Malaysia. In general, stimulant-using MSM trust their peers, especially former stimulant-drug users in disclosing their drug use and sexual behaviors. Currently, majority of stimulant-using MSM use various gay dating apps and social media such as Twitter to advertise and seek chemsex partners (Lim et al., 2018). A low-threshold, community-based intervention using social media engagement may be effective in reaching this subpopulation of MSM.

2. Materials and methods

2.1 Study participants and data collection

Participants will be recruited from Malaysia using advertisements posted on Twitter, Facebook and WhatsApp and mobile dating apps that target MSM communities (e.g., Grindr and Hornet). Interested participants who clicked on the advertisement will be directed to an eligibility screening form via a secure, web-based electronic data capture system.

Potential participants will fill in a brief eligibility survey. The inclusion criteria include:

- 1. Being biologically male
- 2. 18 years old or older
- 3. Having engaged in 'chemsex' with other men in the past 12 months (defined as taking crystal methamphetamine, GBL/GHB, or ecstasy/MDMA)
- 4. Capable of understanding and reading Malay or English
- 5. Willing to be contactable by WhatsApp for follow-up surveys
- 6. Able to provide online consent

Exclusion criteria:

MSM who are currently in drug rehabilitation, receiving treatment for drug abuse, actively engaging in narcotics anonymous or other modes of behavioural intervention-based treatment. Participants who are not eligible will be thanked for their interest. Those who are eligible will proceed to read an online consent form. The nature and the purpose, risk and benefits of participating in the study will be stated in the consent form. The participants who are eligible and provided online consent for the current study will proceed to complete a set of questionnaires which include their sociodemographic information, eASSIST lite (electronic Alcohol, Smoking and Substance Involvement Screening Test), the University of Rhode Island Change Assessment Scale (URICA) and Depression, Anxiety and Stress Scale - 21 Items (DASS-21).

After completion of the survey, participants will be randomized to receive the online intervention (ASSIST-Brief Intervention followed by Chemsex Care Plan) or the self-help guide on substance use published by the World Health Organization (see Figure 2). Participants will be able access the study website with individual ID/password to complete the behavioral assessment at 6-week and 12- week follow up. Participants will be reimbursed RM50 voucher for the completion of each online survey. Participants who have completed all surveys will be asked at the end of the study if they would be interested in participating in a future study of which they will be informed of the nature, purpose and potential harm and benefits. Interested participants' contacting information within this study will be stored in a secure encrypted file for future communication, while participants who do not wish to participate in the future study will have non-essential information (identifiers, contact information etc) deleted at the end of the study.

2.2. Study instruments

Sociodemographic and HIV/STI/Hepatitis C & B risk information

A socio-demographic form is created to obtain social and demographical information regarding the participants. In this section, subjects are required to provide information such as age, gender, ethnicity, preferred language, employment status, HIV testing history, HIV and STI status. Additionally, participants will be asked a few questions on HIV risk behaviors, such as condomless anal intercourse with regular/casual partners and number of sexual partners in the past 30 days.

eASSIST (electronic Alcohol, Smoking and Substance Involvement Screening Test)

The eASSIST is an electronic version of screening tool based on the Alcohol, Smoking and Substance Involvement Screening Test (ASSIST) which was developed by the World Health Organization. It is an 8-item clinician administered questionnaire developed for the World Health Organization (WHO) by an international group of substance abuse researchers to detect psychoactive substance use and related problems in primary care patients (Humeniuk et al., 2010). The ASSIST screens for lifetime and current (within the past three months) substance use of 10 different substances (tobacco, alcohol, cannabis, cocaine, amphetamine-type stimulants, inhalants, sedatives/sleeping pills, hallucinogens, opioids and 'other' drugs). The ASSIST has good concurrent, construct, predictive and discriminative validity, including the development of cut-off scores (Ali et al., 2002; Humeniuk and Ali, 2006; Newcombe et al., 2005; Humeniuk et al., 2008; Khan et al., 2011).

Designed for time pressured environments, the eASSIST takes approximately 5 minutes to complete. The eASSIST helps identify the risks associated with substance use and the personalised feedback helps explore options for change. The Malay version has been validated ([name] et al., 2017)

University of Rhode Island Change Assessment Scale (URICA)

The URICA is a self-reported assessment that measures stages of change within an individual, where each subscale (Precontemplation, Contemplation, Action and Maintenance) can be identified though responses given on a 5-point Likert Scale and be combined arithmetically to obtain a second-order score that can be used to assess 'Readiness to Change' in beginning a treatment. The scale was developed by the University of Rhode Island (DiClemente & Hughes, 1990) and has been validated in Bahasa Malaysia (Abdul Ghani, Amat & Abdullah, 2019). The URICA Scale helps in identifying the willingness of participants to engage in treatment and prompts the development of appropriate interventional treatments.

Depression, Anxiety and Stress Scale (DASS-21)

The DASS-21 is a 21-item questionnaire developed by Lovibond & Lovibond (Henry & Crawford, 2005; Lovibond and Lovibond, 1995). It is an abbreviated version of the original 42-item DASS-42 questionnaire developed by the same author. DASS-21 is a simple and concise self-administered tool that is used for the screening of depression, anxiety and also stress. DASS-21 has 7 items per each domain of depression, anxiety and stress. It has been

validated in many languages, including into the Malay language (Musa, 2007). The higher the total scores for each domain reflect the severity of the respective domains. The severity score for depression in DASS-21 are stratified into normal (0-9 scores), mild (10-13 scores), moderate (14-20 scores), severe (21-27 score), and extremely severe (28 scores or more).

2.3. Randomization, experimental conditions and follow-up

Participants who agree to the follow-up study are sent a link and a password (unique password for each participant) to log onto the study website. Those logging on are randomized in 1:1 ratio with no stratification by using computerized generated random online (www.randomization.com) to receive their respective materials. Those assigned to the intervention condition are provided with the online intervention (see part 3) with Brief Intervention (FRAME model) and The Chemsex Care Plan, developed from the chemsex counsellor health clinic from the renowned sexual (56 Street)(https://www.[name].org/care-plan). Those assigned to the control group will be provided Self-care interventions for health toolkits from World health Organization (WHO) for the first three months. After three months, the control group will be provided with a link to access the The Chemsex Care Plan.

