2.4. Data analysis

2.4.1. Outcome variables

The primary outcome variable is the eASSIST (eASSIST; measured at baseline and 12-week follow-up) which indicates stimulant use severity (Gryczynski et al., 2015). The secondary outcome variables, number of days stimulants used in the last 30 days and the Depression, Anxiety and Stress Scale - 21 Items (DASS-21) will be measured at baseline, 6-week and 12-week follow-up. Among HIV-negative participants, willingness to access PrEP and utilization of PrEP will be assessed while among HIV-positive participants, linkage to HIV services and adherence to ART will be assessed at the 12-week follow up. Additionally, data on utilization of HIV/STI services at the community-friendly clinics will be extracted from the HIV/STI monitoring database by Malaysian AIDS Council using the unique client ID.

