As part of the study, a list of FAQ will serve as an avenue for participants who wish to have quick answers to their questions. A pre-set of questions and answers regarding the benefits and harms of stimulant drug use, harm reduction, existing support services will be compiled and laid out in a simple format. A hotline number will be available on the website for research team to answer questions related to the study at designated time during weekdays. Participants will be reminded by WhatsApp message to conduct the follow-up surveys. All intervention materials will be delivered online; there will be no physical interaction between participants and research team members. No personal identifying information such as names or identification number will be collected from the participants. Instead, unique ID number will be used to identify the participants. Reminder message sent to participants will not reveal participant's status of participating in a study pertaining drug use and HIV.

Online Informed consent will be obtained before participants are enrolled to the study. Participants will be informed of the study design, study procedure and duration, potential risk and benefits of the study. Furthermore, participants will be asked not to reveal any identifying information such as their name and location during the brief intervention. Permission to audio record the brief intervention will be obtained from the participant before beginning of the intervention. The main purpose of the audio recording to verify and evaluate the counseling session and ensure that caseworkers' administration of the Brief Intervention according to the study protocol; all identifying information will be removed prior to review and recordings will be deleted after verification data has been obtained.

5. Adaptation Process

Experts in intervention development and delivering HIV prevention and substance abuse treatment services to stimulant using MSM will be formally engaged. The research team will include a psychiatrist, a public health researcher, a master's-level project director, and two external experts from University of Adelaide and National Cheung Kung University. The research team will conduct bi-monthly meetings with the local community members and services providers to modify the intervention for application in a community setting.

Training of case workers. Case workers from the CBO will undergo formal training in the following:

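### Control access to the Chemsex Care Plan is set by elapsed time in one place and by study end in another, and neither is tied to the 12-week survey, so a late control survey can follow release of one intervention component

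*Protocol*

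**What the plan says.** Two current places in the protocol say when Group B gains the Care Plan.

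- **Section 2.3** gives controls the WHO toolkit "for the first three months" and continues: "After three months, the control group will be provided with a link" to the Care Plan.
- **Study Synopsis, intervention and control groups**, says of Group B: "Participant is encouraged to use the toolkit to manage their drug use for 12 weeks". It continues: "Similar to Group A, they will then be asked to complete a follow-up survey after 6 weeks and 12 weeks". It then says: "After the end of the study, they will be given access to the Chemsex Care Plan".

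Four other places bear on the consequence.

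- **Section 2.4.1:** "The primary outcome variable is the eASSIST (eASSIST; measured at baseline and 12-week follow-up". Days of stimulant use in the last 30 days and DASS-21 are also taken at week 12.
- **Section 2.1** has participants log on to the study website themselves to complete each follow-up. **Section 4** adds: "Participants will be reminded by WhatsApp message to conduct the follow-up surveys".
- **Section 2.4.2** fits mixed models to every observation available at each time point.
- **Section 3** defines the tested intervention as two components: the peer-delivered Brief Intervention and the self-directed Care Plan.

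**The concern.** The control condition should stay unchanged until the primary outcome has been collected. In Section 2.3 it changes on elapsed time, and nothing there refers to whether the man's 12-week survey is in. Self-completed online surveys prompted by reminders can arrive late. A late Group B response may then describe a man who already has part of the tested intervention.

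Group A has the Care Plan from the start, so only the control arm is exposed. Any benefit to exposed controls would narrow the difference between the arms at the primary time point. The two access statements also leave site staff and the webmaster unsure which event opens the link.

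**Working it through.** The plan gives no figure for the gap between survey and release, for the share of late surveys, or for the effect of the Care Plan alone. There is therefore no stated figure to reproduce on this point. The sample size calculation in Section 2.4 is not in dispute here.

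**Step 1. When is the survey due?** 12 weeks × 7 = day 84.

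**Step 2. When is the link released under Section 2.3?**

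- If three months is a loose way of saying 12 weeks: day 84. Gap: 84 − 84 = 0 days.
- If three calendar months, shortest case (1 February to 1 May): 28 + 31 + 30 = 89 days. Gap: 89 − 84 = 5 days.
- If three calendar months, longest case (1 July to 1 October): 31 + 31 + 30 = 92 days. Gap: 92 − 84 = 8 days.

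The calendar-month gap stays within 5 to 8 days for every start date in the planned study period.

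**Step 3. When is the link released under the synopsis?**

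- If the end of the study is the man's own last survey, release follows the survey and the two passages nearly agree.
- If it is each man's scheduled end at 12 weeks, the trigger is again elapsed time.
- If it is closure of the trial, release could come long after three months for men who enrol early, and the passages conflict.

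The text does not choose between these.

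**Step 4. How much of each outcome's recall could be exposed?** Assume, for illustration only, a survey completed 14 days late, on day 98. The assumption is not from the documents.

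| Release day | Days of possible access | eASSIST, three-month recall | Days of use, 30-day recall | DASS-21, past week |
|---|---|---|---|---|
| 92 | 98 − 92 = 6 | 6/92 = 7% | 6/30 = 20% | 6/7 = 86% |
| 89 | 98 − 89 = 9 | 9/89 = 10% | 9/30 = 30% | all 7 days |
| 84 | 98 − 84 = 14 | 14/84 = 17% | 14/30 = 47% | all 7 days |

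The recall periods come from Section 2.2 and Appendix A (eASSIST), Section 2.4.1 (days of use) and Appendix C (DASS-21). The percentages are shares of the recall window after release. They are not effects, because a man must still open the link, use the material and change his behaviour. They show only the ordering: eASSIST is least exposed and DASS-21 most.

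**Step 5. Can the bias be sized?** It would depend on the share of Group B surveys completed after release and on the effect of the Care Plan alone over a few days. Neither is in the documents, so the calculation stops here.

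**The case against.** **The passages may mean the same thing.** The synopsis lists toolkit, surveys, then access, and Section 2.3 may simply describe 12 weeks as three months. This largely stands if the end of the study is each man's own follow-up. It does not remove the point: Section 2.3 still names elapsed time as the trigger, and reading three months as 12 weeks cuts the gap to zero.

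**Survey windows and late-data rules belong in an analysis plan.** Agreed, and their absence is not criticised. The time at which the comparator changes is a protocol matter, and this protocol states it in two ways.

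**After three months may be an earliest time, not an automatic release.** That is possible, but the text does not say so, and nothing in it makes release wait for the survey.

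**Stronger readings that a reader might infer:**

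- *That the 12-week control data are contaminated generally.* They are not. On every reading, a survey completed when due is not preceded by a meaningful period of access.
- *That late controls have received the intervention.* They would have been sent a link to one of its two components, without the Brief Intervention.
- *That the trial loses substantial power.* A marked loss appears only if one assumes that many men respond late and that a few days of one self-directed component give most of the effect assumed for the whole package. No source in the documents supports either assumption, and the three-month recall of eASSIST argues against the second.

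**Conclusion.** The point holds as a minor, inexpensive improvement. The protocol gives two access triggers, and neither is expressly linked to collection of the 12-week survey. The Section 2.3 trigger falls 0 to 8 days after that survey is due. A late Group B survey can therefore follow release of one component, and the planned analysis would not distinguish it.

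Any resulting bias is confined to the control arm. It runs towards no difference, provided the Care Plan is beneficial rather than harmful. It is probably small for eASSIST, the primary outcome, and larger for days of use and DASS-21. If few men respond late, it is negligible. Its size cannot be derived from the documents, and no loss of power should be attached to it.

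**What to change.** 1. Reconcile the Study Synopsis and Section 2.3 into one statement. It should say whose end of study is meant and how release of the link relates to collection of that participant's 12-week survey, so that the outcome is collected before the comparator changes. The access time itself is for the sponsor to choose.
2. Store two dates for each Group B participant: completion of the 12-week survey and release of the link. Section 5 already plans to record website activity and Care Plan usage, so this should add little.
3. Add a sensitivity analysis that excludes Group B 12-week scores collected after release. It removes late responders from one arm only, so it should be read beside the main analysis and not replace it.

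The cost is one sentence, two stored dates and one extra model run per outcome. Depending on the sponsor's choice, men who respond late may gain access slightly later.
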